7.7 PROPHYLACTIC MEDICATIONS, TREATMENTS, AND PROCEDURES

Not applicable to this study.

7.8 RESCUE MEDICATIONS, TREATMENTS, AND PROCEDURES

Not applicable to this study.

7.9 PARTICIPANT ACCESS TO STUDY AGENT AT STUDY CLOSURE

Not applicable to this study.

8. ASSESSMENT OF SAFETY

8.1 SPECIFICATION OF SAFETY PARAMETERS

Safety assessments include physical examinations, vital signs, clinical laboratory tests, solicitation of TEAEs and concomitant medications, and general medical evaluations.

8.1.1 DEFINITION OF ADVERSE EVENTS (AE)

TEAEs in the eCRF will be classified according to the most recent US FDA definitions and in a manner consistent with ICH guidelines. As such the following definitions will be used:

An adverse event (AE) is any unfavorable and unintended sign, symptom, or disease temporally associated with the use of an investigational (medicinal) product (IP) or other protocol-imposed intervention, regardless of attribution. An AE may include intercurrent illnesses or injuries that represent an exacerbation (increase in frequency, severity, or specificity) of preexisting conditions (e.g., worsening of asthma).

Whenever possible, it is preferable to record a diagnosis as the TEAE term rather than a series of symptoms relating to a diagnosis. In order to classify TEAEs and diseases, preferred terms will be assigned by the Sponsor to the original terms entered on the eCRF, using the Medical

Dictionary for Regulatory Activities (MedDRA).

8.1.2 DEFINITION OF SERIOUS ADVERSE EVENTS (SAE)

According to the ICH Guidelines for Good Clinical Practice (E6), an SAE is any untoward medical occurrence during the course of a clinical investigation that is characterized by 1 or more of the following:

- Results in death
- Is life threatening
- Requires nonscheduled (not routine or planned) subject hospitalization or prolongation of existing hospitalization for ≥ 24 hours and admission to the hospital
- Results in persistent or significant disability/incapacity
- Is a congenital anomaly/birth defect
- Is an important medical event, defined as an event that does not fit one of the other outcomes, but may jeopardize the subject and may require medical or surgical intervention (treatment) to prevent one of the other outcomes. Examples include allergic bronchospasm (a serious problem with breathing) requiring treatment in an emergency room, serious blood dyscrasias (blood disorders), or seizure/convulsion that does not result in hospitalization. The development of drug dependence or drug abuse would be other examples of important medical events.

All SAE information must be recorded on the SAE form approved by the Sponsor. Additional follow-up information (e.g., test results, autopsy, and discharge summary) may be requested to supplement the SAE report form and can be attached as de-identified records.

8.1.3 DEFINITION OF UNANTICIPATED PROBLEMS (UP)

An unanticipated problem is defined as, in general, any incident, experience, or outcome that meets all of the following criteria:

- Unexpected in terms of nature, severity, or frequency given (a) the research procedures that are described in the protocol-related documents, such as the IRB-approved research protocol and informed consent document; and (b) the characteristics of the participant population being studied;
- Related or possibly related to participation in the research (“possibly related” means there is a reasonable possibility that the incident, experience, or outcome may have been caused by the procedures involved in the research); and
- Suggests that the research places participants or others at a greater risk of harm (including physical, psychological, economic, or social harm) than was previously known or recognized.

8.2 CLASSIFICATION OF AN ADVERSE EVENT

8.2.1 SEVERITY OF EVENT

The Investigator will assess TEAEs for severity utilizing the “Guidance for Industry: Toxicity Scale for Healthy Adult and Adolescent Volunteers Enrolled in Preventive Vaccine Trials”. This

toxicity scale is presented in [Appendix 1](#). Laboratory values not listed on the toxicity scale will be assessed for severity by the clinical Investigator.

8.2.2 RELATIONSHIP TO STUDY AGENT

The relationship of the study treatment to a TEAE will be determined by the Investigator based on the following definitions:

1. Not Related

The TEAE is not related if (1) exposure to the investigational product (or placebo) or administration of the study injection has not occurred **or** (2) the occurrence of the TEAE is not reasonably related in time **or** (3) the TEAE is considered related to another event or product not associated with the investigational product (or placebo) or the study injection.

2. Unlikely Related

The TEAE is unlikely related if (1) the TEAE is unlikely related in time **or** (2) the TEAE is considered unlikely to be related to use of the investigational product (or placebo) or study injection (i.e., there are no facts [evidence] or arguments to suggest a causal relationship).

3. Possibly Related

The TEAE is possibly related if (1) the investigational product (or placebo) or the study injection and TEAE are considered reasonably related in time **and** (2) the TEAE could be explained by causes other than exposure to the investigational product (or placebo) or administration of the study injection.

4. Probably Related

Exposure to the investigational product (or placebo) or administration of the study injection and TEAE are probably related if (1) the investigational product (or placebo) or study injection and TEAE are considered reasonably related in time **and** (2) the investigational product (or placebo) or study injection is more likely than other causes to be responsible for the TEAE **or** is the most likely cause of the TEAE.

8.2.3 EXPECTEDNESS

The Sponsor will be responsible for determining whether a TEAE/SAE is expected or unexpected. A TEAE/SAE will be considered unexpected if the nature, severity, or frequency of the event is not consistent with the risk information previously described for the study agent in the IB or is not listed in the IB at the specificity or severity that has been observed.

8.3 TIME PERIOD AND FREQUENCY FOR EVENT ASSESSMENT AND FOLLOW-UP

The reporting period for TEAEs starts after the injection of study medication on Day 1 and ends after the final study visit.

TEAEs must be followed until resolution by the Investigator. Resolution is defined as the return to baseline status or stabilization of the condition with the expectation that it will remain chronic. TEAEs that are not serious and are ongoing at the subject's last visit will be followed until the

study close-out visit, if requested. Serious adverse events that are not resolved or stabilized during this time period will be followed until resolution or stabilization.

8.4 REPORTING PROCEDURES

8.4.1 ADVERSE EVENT REPORTING

The Investigator is responsible for reporting TEAEs to the Sponsor and IRB according to the protocol as well as 21 Code of Federal Regulations (CFR) part 50, part 56, and part 312. The Investigator is responsible for ensuring accurate TEAE information is reviewed and recorded in the subject source and the TEAE eCRF in a timely manner. The Sponsor is responsible for submitting reports of TEAEs associated with the use of study medication that are both serious and unexpected to the FDA according to 21 Code of Federal Regulations (CFR) 312.32. All Investigators participating in ongoing studies with the study medication will receive copies of these reports from the Sponsor for prompt submission to their IRB/EC according to their institution’s requirements.

8.4.2 SERIOUS ADVERSE EVENT REPORTING

The Investigator is responsible for reporting SAEs to the Sponsor and IRB according to 21 Code of Federal Regulations (CFR) part 50, part 56, and part 312. The Investigator and Samumed will manage SAEs according to the study document “Guidelines For The Management Of Serious Adverse Events (SAEs) And Pregnancies”.

All SAEs must be reported as described in the study manual by the Investigator, Study Coordinator, other designated study personnel, or Clinical Research Associate within 24 hours of notification of the SAE. The Investigator or designee should submit the SAE report to the Samumed Study SAE email address: [contact] or [contact]. Follow-up information must be detailed in a follow-up SAE report and reported to the Samumed Study SAE email address or fax number as it becomes available. The Investigator also must report all SAEs promptly to the appropriate IRB/EC as required by the institution. Sponsor contact information for questions regarding SAE reporting is provided in [Table 1](#).

Table 1: Sponsor Contact Information for Questions on SAE Reporting

Primary Contact	Alternative Contact
[REDACTED]	[REDACTED]
[REDACTED] [REDACTED]	[REDACTED] [REDACTED]
[REDACTED] [REDACTED]	[REDACTED] [REDACTED]
[REDACTED] [REDACTED]	[REDACTED] [REDACTED]

8.4.3 UNANTICIPATED PROBLEM REPORTING

Incidents or events that meet the criteria for unanticipated problem require the creation and completion of an UP report. It is the site investigator’s responsibility to report UPs to their IRB and to the Sponsor. The UP report will include the following information:

- Protocol identifying information: protocol title and number, PI's name, and the IRB project number;
- A detailed description of the event, incident, experience, or outcome;
- An explanation of the basis for determining that the event, incident, experience, or outcome represents an UP; and
- A description of any changes to the protocol or other corrective actions that have been taken or are proposed in response to the UP.

To satisfy the requirement for prompt reporting, UPs will be reported using the following timeline:

- UPs that are SAEs will be reported to the IRB and to the Sponsor within 24 hours of the investigator becoming aware of the event.
- Any other UP will be reported to the IRB and to the Sponsor within the IRB-required reporting timeframe.
- All UPs should be reported to appropriate institutional officials (as required by an institution's written reporting procedures) and IRB within the timeframe specified by the institution procedures and IRB.

8.4.4 EVENTS OF SPECIAL INTEREST

Not applicable to this study.

8.4.5 REPORTING OF PREGNANCY

Although pregnancy is not a formal SAE, if a study participant or the partner of a study participant becomes pregnant while the study participant is on study, the pregnancy is to be reported via SAE reporting procedures. The Investigator and Samumed will manage reporting of pregnancies according to the study document "Guidelines For The Management Of Serious Adverse Events (SAEs) And Pregnancies".

8.5 STUDY HALTING RULES

Not applicable to this study.

8.6 SAFETY OVERSIGHT

Clinical safety oversight will be performed by centralized review conducted by Medical Monitors per the Medical Monitoring Plan. In addition, on-site review will be conducted by Clinical Research Associates.

9. CLINICAL MONITORING

All aspects of the study will be monitored by the Sponsor or the Sponsor's designees with respect to current Good Clinical Practice (GCP) and Standard Operating Procedures (SOPs) for compliance with applicable government regulations. It is the responsibility of the Investigator to provide all study records, including eCRFs and source documents among other records, for review and inspection by the clinical monitor.

Clinical monitoring will be performed per the Clinical Monitoring Plan. Clinical monitors will

periodically evaluate the progress of the study, including the verification of appropriate consent form procedures and the verification of the accuracy and completeness of eCRFs. Clinical monitors will also ensure that all protocol requirements, applicable US FDA regulations, other regulatory requirements, and the Investigator's obligations are being fulfilled.

Centralized data monitoring will be performed per the Centralized Data Monitoring Plan in order to periodically evaluate study progress and risks. A regular report of risks will be utilized together with on-site and off-site centralized data monitoring to direct overall monitoring focus and activities to the areas of greatest risk which have the most potential to impact subject safety and data quality.

The accuracy of the data will be verified by reviewing the documents described in [Section 11](#).

10. STATISTICAL CONSIDERATIONS

10.1 STATISTICAL AND ANALYTICAL PLANS

This section describes the planned statistical analyses in general terms. A complete description of the statistical analyses will be specified in a statistical analysis plan (SAP), finalized prior to database lock.

10.2 STATISTICAL HYPOTHESES

No formal hypotheses are being tested in this study.

10.3 ANALYSIS DATASETS

Full Analysis Set (FAS): All subjects who are randomized and receive a study injection. Full analysis set is used to describe the analysis set which is as complete as possible and as close as possible to the intent-to-treat ideal of including all randomized subjects.

Modified Full Analysis Set (mFAS): FAS subjects who receive a protocol specified injection. Subjects who are administered a treatment that is not prescribed by the protocol will be excluded from this analysis set.

Per-Protocol Analysis Set (PPAS): mFAS subjects who complete the study and do not have any major protocol deviations.

Safety Analysis Set (SAS): All subjects who receive a study injection.

10.4 DESCRIPTION OF STATISTICAL METHODS

10.4.1 GENERAL APPROACH

For continuous variables, the number of subjects in the analysis, mean, standard deviation (SD), median, minimum, and maximum will be reported. All categorical endpoints will be summarized using frequencies and percentages.

10.4.2 ANALYSIS OF THE PRIMARY ENDPOINT(S)

Analysis of covariance (ANCOVA) will be used to estimate the least squares difference in the change in weekly average of daily pain NRS, WOMAC Pain, WOMAC Function, and medial

JSW adjusting for baseline value. Change will be assessed from baseline between each treatment group and the vehicle placebo group. Unadjusted 95% confidence intervals and P values will be reported.

Multiple Comparison Procedure Modelling (MCP-Mod) will estimate SM04690 dose response compared to vehicle using the results of the primary efficacy endpoint analyses.

As the study is stratified based upon known clinical phenotypes of OA, all primary efficacy analyses will be completed in three subject populations: 1) subjects with unilateral symptomatic OA, 2) subjects with unilateral symptomatic OA and without widespread pain ($WPI \leq 4$ and $SSQ2 \leq 2$), and 3) all subjects.

10.4.3 ANALYSIS OF THE SECONDARY ENDPOINT(S)

The number and percent of subjects experiencing TEAEs will be summarized by seriousness, severity, and relationship for each treatment group.

ANCOVA will be used to estimate the least squares difference in the change in Patient Global Assessment adjusting for baseline value. Change will be assessed from baseline between each treatment group and the vehicle placebo group. Unadjusted 95% confidence intervals and P values will be reported.

MCP-Mod will estimate SM04690 dose response compared to vehicle using the results of the secondary efficacy endpoint analyses.

As the study is stratified based upon known clinical phenotypes of OA, all secondary efficacy analyses will be completed in three subject populations: 1) subjects with unilateral symptomatic OA, 2) subjects with unilateral symptomatic OA and without widespread pain ($WPI \leq 4$ and $SSQ2 \leq 2$), and 3) all subjects.

10.4.4 SAFETY ANALYSES

Safety analyses will be performed on subjects who receive a study injection. Safety assessments include physical examinations, vital signs, clinical laboratory tests, solicitation of TEAEs and concomitant medications, and general medical evaluations. No formal statistical analyses are planned. Safety will be evaluated based on the incidence, seriousness, severity, and relationship of TEAEs and by changes in clinical laboratory parameters and vital signs, relative to baseline. Changes from baseline in the amount and duration of NSAID usage will be monitored.

10.4.5 BASELINE DESCRIPTIVE STATISTICS

For comparisons with baseline within each analysis population, baseline is defined as the last value recorded for any given parameter prior to study medication injection at Day 1.

10.4.6 PLANNED INTERIM ANALYSES

Not applicable to this study.

10.4.6.1 SAFETY REVIEW

Medical monitoring of study safety assessment data will be performed during periodic safety reviews detailed in the Medical Monitoring Plan.

10.4.6.2 EFFICACY REVIEW

Not applicable to this study.

10.4.7 EXPLORATORY ANALYSES

Change from baseline will be summarized with descriptive statistics at Weeks 4, 8, 12, 16, and 20 for WOMAC pain subscore, WOMAC function subscore, and Patient Global Assessment; at Weeks 4, 8, 12, 16, 20, and 24 for WOMAC total score, and KOOS (five subscales [Pain, Symptoms, ADL, Sport/Rec and QOL] as well as aggregate scores KOOS₄ and KOOS₅); and at Weeks 4, 12, and 24 for Physician Global Assessment. Change from baseline will also be statistically described for weekly KOOS-PS and weekly averages of daily pain NRS (aside from Week 24). Change over time in weekly NSAID usage will also be assessed at every week.

ANCOVA will be used to estimate the least squares difference in the change from baseline in exploratory outcomes between each of the four active treatment groups and the vehicle group, adjusted for baseline value. Additionally, ANCOVA will be used to estimate the least squares difference in the change from baseline in all outcomes (including primary and secondary) between the vehicle group and the sham group, adjusted for baseline value. Unadjusted 95% confidence intervals and P values will be reported.

MCP-Mod will estimate SM04690 dose response compared to vehicle using the results of the exploratory efficacy endpoint analyses.

As the study is stratified based upon known clinical phenotypes of OA, all exploratory efficacy analyses will be completed in three subject populations: 1) subjects with unilateral symptomatic OA, 2) subjects with unilateral symptomatic OA and without widespread pain ($WPI \leq 4$ and $SSQ2 \leq 2$), and 3) all subjects.

Evaluation of subject awareness of randomized treatment given and the success of blinding in this trial will be estimated using an appropriate categorical analysis. Specifically, the percentage of subjects accurately identifying the assigned treatment group will be estimated.

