Two DLTs were reported on the trial, both occurring in the 0.07 mg treatment group (increased knee pain and tachycardia paroxysmal [also an SAE as noted above]). The DLT of increased knee pain was considered probably related to treatment by the reporting investigator.

Single intra-articular injections of SM04690 at doses of 0.03 mg, 0.07 mg, and 0.23 mg in a 2 mL suspension into the target knee joint appeared to be safe and well-tolerated in subjects with moderately to severely symptomatic OA of the knee. No clinically significant safety concerns or differences between active and placebo treatment groups were noted with regard to AEs, clinical laboratory results, vital signs, ECGs, assessment of bone loss, assessment of bone marrow edema, or assessment of inflammatory cytokines.

An interim analysis of the phase 2 SM04690-OA-02 study was performed in October 2016 after all subjects completed their Week 26 visit. Summarizing the safety events occurring within these 26 weeks and summarized in the interim analysis, 8 SAEs have been reported in 7/452 (1.5%) subjects. The SAEs reported have been Hypertensive crisis, Cholecystitis acute, Gall bladder adenocarcinoma, Uterine prolapse, Diverticulitis, Patella fracture, Osteoarthritis (of the hip), and Non-cardiac chest pain. These events were felt to be either not related or unlikely related to study medication by investigator assessment.

Study Placebos

The 2 possible placebo injections in this study will be either 2 mL of vehicle, which is the inactive substance carboxymethylcellulose sodium and polysorbate 80, or a 0 mL sham injection. The inactive substance carboxymethylcellulose sodium and polysorbate 80 is often used as a food or drug additive. Potential risks associated with carboxymethylcellulose sodium and polysorbate 80 include allergic reaction and hypersensitivity.

The placebo sham injection contains no substance and has the same risks associated with the knee joint injection which include bleeding, bruising, infection, pain at the injection site, swelling of the knee, and/or injury to knee joint.

Risks of Injection

Risks associated with knee joint injection include bleeding, bruising, infection, pain at the injection site, swelling of the knee, and/or injury to knee joint.

Risks of Topical Anesthetics

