The Investigator completing the Physician Global Assessment must sign/initial and date the source document to indicate that the assessment is reported accurately. A study staff member will record the Physician Global Assessment score in the eCRF. The score is determined by measuring the distance (mm) between the “Very Good” anchor and the Investigator’s mark, providing a range of scores from 0 to 100.

The Physician Global Assessment of Disease Activity questionnaires will be provided by the Sponsor and may not be reproduced.

Evaluation of Success of Blinding

At Day 1 (post intra-articular injection) and Week 24 (EOS)/ET, subjects will complete a questionnaire on paper as to which treatment arm of the study they believe they were assigned to in order to evaluate the effectiveness of blinding. The questionnaire will capture responses of “Study drug injection,” “Injection of 2 mL inactive vehicle substance,” “Needle insertion into the knee with no vehicle substance injected,” and “Do not know.”

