10.6.2 EVALUATION OF SUCCESS OF BLINDING

Subjects will be queried regarding the perceived effectiveness of blinding. Details of this analysis will be provided in the SAP.

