7.2. ANCOVA Model for Continuous Efficacy Outcomes

ANCOVA models will be used for all continuous efficacy outcome measures summarized by change from baseline in order to test the following four hypotheses:

$$H_0: (\beta_i - \beta_0) = 0$$

$$H_A: (\beta_i - \beta_0) \neq 0, \text{ where } i = 1,2,3,4$$

In the statement above, β is the least squares estimate in the change in the continuous efficacy outcome from baseline at each timepoint (where β_0 is the estimate for vehicle), and i represents each of the four SM04690 treatment groups.

Least squares estimate of difference between each treatment group and placebo in the change in the continuous efficacy outcome from baseline at each timepoint, adjusted for baseline value, will be reported along with unadjusted 95% confidence intervals and P values.

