7.5.3. Subject Perception of Treatment

The following contingency table will be prepared to evaluate the subjects' perception of treatment received at Day 1 and at Week 24.

Assignment	Guess				Total
	SM04690 (1)	Vehicle (2)	Sham (3)	Don't Know (4)	
SM04690 (1)	$n_{11} (P_{1 1})$	$n_{12} (P_{2 1})$	$n_{13} (P_{3 1})$	$n_{14} (P_{4 1})$	$n_{1.}$
Vehicle (2)	$n_{21} (P_{1 2})$	$n_{22} (P_{2 2})$	$n_{23} (P_{3 2})$	$n_{24} (P_{4 2})$	$n_{2.}$
Sham (3)	$n_{31} (P_{1 3})$	$n_{32} (P_{2 3})$	$n_{33} (P_{3 3})$	$n_{34} (P_{4 3})$	$n_{3.}$
Total	$n_{.1}$	$n_{.2}$	$n_{.3}$	$n_{.4}$	N

$P_{ji} = P(\text{guess } j | \text{assigned treatment } i) = \text{probability of guessing treatment } j \text{ when assigned treatment } i$

Bang's Blinding Index (BI) (Bang et al. 2010) will be calculated to determine the percentage of unblinding that is beyond chance.

$$\text{Bang's BI}_i = \left(2 \frac{n_{ii}}{n_{i1} + n_{i2} + n_{i3}} - 1 \right) \times \left(\frac{n_{i1} + n_{i2} + n_{i3}}{n_{i1} + n_{i2} + n_{i3} + n_{i4}} \right),$$

where $\text{BI}_i = 0$ represents random guessing; $\text{BI}_i = 1$ represents complete unblinding;
 $\text{BI}_i = -1$ represents opposite guessing

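### SAP 7.5.3 merges the four SM04690 doses into one blinding row, so unblinding confined to one dose would show at a quarter of its size, and no dose-versus-vehicle comparison of guesses is planned

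*Protocol*

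**What the plan says.** Protocol 7.1.1 has subjects report "which treatment arm of the study they believe they were assigned to". The form offers one study-drug answer, 2 mL vehicle, needle insertion only, and 'do not know'; there is no answer for a particular dose.

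Protocol 10.4.7 states that "the percentage of subjects accurately identifying the assigned treatment group will be estimated". Protocol 10.6.2 leaves the rest to the SAP: "Details of this analysis will be provided in the SAP".

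SAP 7.5.3 sets out a contingency table of "perception of treatment received at Day 1 and at Week 24". It has three assignment rows (SM04690, vehicle, sham) and four guess columns, with counts and row-conditional proportions. Bang's index is then computed for each row and "will be calculated to determine the percentage of unblinding that is beyond chance"; a value of 0 "represents random guessing" and a value of 1 is read as complete unblinding.

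Efficacy is set up at dose level. SAP 7.2 reports the "Least squares estimate of difference between each treatment group and placebo", with four hypotheses, one per dose against vehicle. SAP 7.6 uses MCP-Mod to model dose response on the primary and secondary outcomes. Of the four primary endpoints, weekly Pain NRS, WOMAC Pain and WOMAC Function are patient-reported and medial joint space width is radiographic. The secondary efficacy endpoint, the Patient Global Assessment, is also patient-reported.

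**The concern.** Blinding is checked at a coarser level than efficacy. If subjects on one dose came to recognise that they had active drug, that dose's Week 24 difference in pain or function, and the curve fitted through it, could partly reflect expectation. The question that bears on each efficacy contrast is whether subjects on that dose say 'study drug' more often than subjects on vehicle. The planned table mixes that dose with the three others and attaches no interval to any comparison with vehicle.

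There is a second, related weakness. An index or percentage computed inside one assignment row depends on how people tend to guess as well as on what they know. Only a comparison between rows separates the two.

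**Working it through.** **Inputs.** Protocol 10.5: about 630 subjects, six equal arms. No power, effect size, SD or dropout is given, so 630 itself cannot be reproduced; 630/6 = 105 per arm and 4 × 105 = 420 in the pooled row are simple division and multiplication. Index formula: SAP 7.5.3. The documents give no guess rates, so those below are assumptions shown over a range. The SAP states no interval for the index; a normal-approximation 95% interval is used here as a yardstick, and the SAP's reference value of 0 is taken as given.

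**Index.** (2 × correct/guesses − 1) × (guesses/all) simplifies to BI = pc − pw, the proportion correct minus the proportion wrong, with 'do not know' in the denominator. Its variance is [(pc + pw) − (pc − pw)²]/n.

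**One dose unblinded, three at BI = 0, no 'do not know', 70% correct at that dose.**
- Dose row: BI = 0.70 − 0.30 = 0.40. SE = √[(1 − 0.16)/105] = 0.089. Interval 0.23 to 0.58.
- Pooled row: BI = (0.40 + 0 + 0 + 0)/4 = 0.10. SE = √[(0.84 + 3 × 1)/(105 × 16)] = 0.048. Interval 0.01 to 0.19. Percent correct in the row is (70 + 3 × 50)/4 = 55%.
- Chance that the interval excludes 0: Φ(0.40/0.089 − 1.96) = 99% against Φ(0.10/0.048 − 1.96) = 55%.

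The signal is divided by exactly four and the standard error by about two. Over a range:

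| 'Do not know' | Correct among guessers at that dose | BI, dose row | BI, pooled row | Chance, dose row | Chance, pooled row |
|---|---|---|---|---|---|
| 0% | 65% | 0.30 | 0.075 | 90% | 34% |
| 0% | 70% | 0.40 | 0.10 | 99% | 55% |
| 20% | 70% | 0.32 | 0.08 | 98% | 46% |
| 40% | 70% | 0.24 | 0.06 | 92% | 36% |
| 0% | 90% | 0.80 | 0.20 | almost 100% | 99% |

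The cohort caps in Protocol 7.3.2 add to 600, or 100 per arm. The 70% case then gives a pooled SE of √[3.84/(100 × 16)] = 0.049, z = 2.04 and a chance of about 53%, so little changes.

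**Guessing habit.** Suppose every subject in every arm answers 'study drug', so that guesses carry no information on assignment. The SM04690 row gives BI = (2 × 1 − 1) × 1 = 1, the SAP's label for complete unblinding. The vehicle and sham rows each give (2 × 0 − 1) × 1 = −1. Overall percent correct is 4/6 = 67%. Under other uninformative habits it is 33% (even three-way guessing), 17% (all say vehicle) or 0% (all say 'do not know').

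**Dose minus vehicle.** The difference in the proportion answering 'study drug' is 0 in expectation whenever guesses do not depend on assignment, whatever the habit.
- 70% at one dose against 50% on vehicle, 105 each: SE = √[(0.21 + 0.25)/105] = 6.6 points, z = 20/6.6 = 3.02, about an 86% chance of detection at two-sided 5%. At 65% it is about 60%.
- With Bonferroni over four doses (critical value 2.50) these become about 70% and 39%.
- Width when both proportions are 50%: 1.96 × √(2 × 0.25/105) = 13.5 points either side.

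**The case against.** Several things can fairly be said for the plan, and most of them limit the point.

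- **The protocol sentence does not pool doses.** A reader might infer pooling from Protocol 10.4.7, but it speaks only of the assigned treatment group. The merging is in the row labels of SAP 7.5.3.
- **The plan is more than percent correct.** The SAP gives the full table with row-conditional proportions. Pooled active beside vehicle, and vehicle beside sham, can be read off it, though without an interval. A habit of saying 'study drug' would also show as strongly negative vehicle and sham rows. What cannot be read off is any single dose against vehicle.
- **Not every efficacy comparison is dose by dose on a patient-reported outcome.** Medial joint space width and the Physician Global Assessment are not patient-reported, vehicle against sham involves no active dose, and MCP-Mod fits across doses.
- **Evidence for dose-specific cues is weak.** A reader might point to the two phase 1 DLTs, "both occurring in the 0.07 mg treatment group". One of them, the tachycardia, was judged unrelated, which leaves one related knee-pain event. Protocol 2.3.1 reports no clinically significant differences between active and placebo groups, and Protocol 2.2 reports no obvious dose response in the most frequent adverse events of the earlier phase 2 study. All active doses and vehicle use the same 2 mL volume, and Protocol 6.1.5 shields subjects from seeing the product and procedure. Injectors know the arm, so a route exists, but the documents give no sign that it operates at one dose.
- **The size of the loss depends on the test.** A pooled-active-against-vehicle test would give about 15% against 86% in the 70% scenario, but the SAP plans no such test. On its own index the figures are 55% and 99%.
- **Perception of treatment is an exploratory endpoint**, and assigned dose is known, so dose rows could be produced at reporting without prior specification.

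The last objection stands only in part: a dose-level check added after one dose looks effective is less convincing than one written down beforehand.

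**Conclusion.** The point holds as a modest gap in an exploratory analysis. The four doses share one row in SAP 7.5.3, each row is judged on its own, and no dose-level blinding summary is planned, although efficacy is assessed by dose and mostly on patient-reported measures.

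Unblinding confined to one dose would be diluted to a quarter. In the 65% to 70% scenarios the chance of seeing it on the SAP's index drops from 90–99% to 34–55%. It would be tempting to say that such unblinding is averaged away; that goes too far, since at 90% correct the pooled index is 0.20 with an interval of 0.11 to 0.29. These figures rest on 105 per arm, on the other three doses sitting at the index's zero, and on assumed guess rates. Nothing in the documents shows that any dose is in fact recognisable.

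**What to change.** In SAP 7.5.3:

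- Use six assignment rows (four doses, vehicle, sham) at Day 1 and at Week 24, and keep the pooled SM04690 row.
- For each dose, report the difference from vehicle in the proportion giving the study-drug answer, with a 95% confidence interval, counting 'do not know' in the denominator. Report the same difference for vehicle against sham.
- Treat these differences as the main summary. Percent correct and the within-row index may still be shown, with a note that both depend on guessing habit.
- Read the Day 1 table first, because Week 24 guesses may also reflect benefit. Day 1 cannot capture cues that arise later, so both tables are needed.

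The cost is a few table rows and some SAP wording. No new data are needed, and no protocol amendment, because Protocol 10.6.2 leaves the detail to the SAP. The downside is wider intervals, about ±14 points per dose, and several unadjusted comparisons over four doses and two time points. They should be read descriptively.
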